Study Protocol

Title: Heart rate and Breathing Effects on Attention and Memory (HeartBEAM)

NCT number: NCT05602220

IRB approval date: 5/15/2023

Uploaded date: 12/08/2025

Research Background

As we age, the parasympathetic system declines as the sympathetic system becomes hyperactive. In our previous clinical trial (Nashiro et al., 2023; Yoo et al., 2023), we found that increasing parasympathetic activity through daily practice of slow-paced breathing significantly decreased plasma amyloid- β (A β) in healthy younger and older adults (Min et al., 2023). In healthy adults, higher plasma A β is associated with greater risk of Alzheimer's disease (AD). Our primary goal of the current trial is to extend our initial findings regarding effects of slow-paced breathing on A β . Our secondary objectives are to examine the effects of daily slow-paced breathing on brain structure and the rate of learning.

Research Objectives

The aim of the study is to examine how daily paced breathing affects plasma A β levels and the rate of learning in older adults. Healthy adults aged 50-70 who meet all eligibility criteria will be invited to this study. Participants will be randomly assigned to one of the two conditions: 1) Daily memory and attention training followed by a paced breathing protocol designed to increase relaxation or 2) Daily memory and attention training followed by a paced breathing protocol to increase alertness. Participants will be asked to complete pre and post intervention cognitive testing online, engage in 10 weeks of daily brain training (starting Week 2) and 9 weeks of paced breathing (starting Week 3) at home. They will also be asked to come in for lab visits on Weeks 2, 7 and 12 to provide blood and urine samples to assess amyloid beta levels and to complete magnetic resonance imaging scans to assess perivascular space volume.

Methods and Design

Overview of the study

Timeline	Lab Visit	Home Tasks
Week 1		online consent, home cognitive testing
Week 2	(Visit 1) EEG tasks, questionnaires (Visit 2) MRI, blood & urine samples, cognitive tasks, questionnaires, give heart rate monitoring device	(Training Week 1) cognitive training + resting pulse measures (~40 min/day)
Week 3		(Training Week 2) cognitive + breathing training (~60 min/day)
Week 4		(Training Week 3) cognitive + breathing training (~60 min/day)
Week 5		(Training Week 4) cognitive + breathing training (~60 min/day)
Week 6		(Training Week 5) cognitive + breathing training (~60 min/day)

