The feedback will differ between the two conditions, in that the slow-paced breathing participants will be trained to try to maximize heart rate oscillations while the random-paced breathing participants will be trained to try to avoid heart rate oscillations. In each condition, they will receive a feedback score that is incremented during the session and has a final value at the end of the session. This score will reflect the opposing goals in the two conditions, with larger values for higher heart rate oscillations in the slow-paced breathing condition and larger values for less oscillatory power in the random-paced breathing condition.

Participants in the two conditions will be guided through which breathing paces to use to try to optimize their feedback scores each time they practice. During each 15-min practice session, participants will be guided through five 3-min segments of randomly selected paces from their set of paces. Over time, this set will get smaller, as the app gathers average performance of each pace for that participant and compares it to the other paces and discards those that are clearly worse than the numerically best pace because its 95% confidence interval no longer overlaps with the top ranked pace. Our intention is to find paces that work well for each individual to achieve their goal.

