During the intervention, each participant's progress will be facilitated by the app that will send reminders when they fail to complete practices. Progress will be monitored by a group of researchers; if participants fall behind on practice, we will contact them by email, phone, or video calls (e.g., Zoom) for us to check if they have any problems with any aspects of the study, such as device and internet issues. There will be no opportunities to make up sessions and if participants only complete part of a session one day, they will start at the beginning of a session the next time they practice. We anticipate high compliance with practice, as in our prior 5-week HRV biofeedback study, older participants averaged **over 100%** of the practice we asked them to complete (and by week 3, this was 40 min/day of biofeedback). In that study, we did not ask them to do more than 40 min/day so this is an indicator that they enjoyed it or felt they were getting something worthwhile from it. Thus, we have some experience indicating that the HRV-biofeedback is something that participants can do every day. In addition, Lumosity is a highly engaging platform and we anticipate that older adults will enjoy the activity.

Week 7 - Lab Visit 3 (around 2 hours):

Participants will be asked to complete the same assessments as in Visit 2 (i.e., MRI, blood draw, urine collection, blood pressure measurement, questionnaires).

Week 12 - Lab Visit 4 (around 2 hours):

Participants will be asked to complete the same assessments as in Visit 1 except that we will not repeat the following cognitive tests: MINT, FAQ and MoCA.

Week 12 - Lab Visit 5 (around 2 hours)

Participants will be asked to complete the same assessments as in Visit 2. They will also be asked to return their devices.

A few days after Visit 2, 3, and 5, participants will be asked to complete the post blood draw questionnaire to report any adverse events associated with the blood draw, if any. We will report to the IRB if the responses to any of the questions were the most negative response option. For example, one of the questions is “do you notice any bleeding after your session (on your way home or at home)? The response options are 1) no bleeding, 2) a little (perhaps a few drops, 3) yes (needed a new bandage). We will report to the IRB when the response was #3.

Week 12 - Home Tasks:

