Statistical Analysis Plan (SAP)

Study Title	Heart rate and Breathing Effects on Attention and Memory (HeartBEAM)
Principal Investigator	[name] Professor of Gerontology, Psychology and Biomedical Engineering University of Southern California Los Angeles, California, USA
Protocol identification number	UP-21-00357
ClinicalTrials.gov identifier	NCT05602220
Author	[name] Research Associate [name] of Southern California Los Angeles, California, USA
Version	Draft 0.1
Date	09/02/2025

1. Objectives and hypotheses

In our previous HRV-ER trial (NCT03458910), four weeks of daily slow-paced breathing designed to enhance parasympathetic activity reduced plasma A β levels in both younger and older adults. The current study aimed to extend those findings in adults aged 50 to 70 years using a 10-week intervention with three assessment time points. Secondary objectives included examining the effects of slow-paced breathing on brain structure (i.e., perivascular space and hippocampal volumes) and cognitive performance. We hypothesized that the 10-week slow-paced breathing intervention would reduce plasma A β levels and lead to improvements in brain structure and cognitive performance.

2. Sample Size & Power consideration

For plasma A β , we estimated reliability using correlations between pre- and post-intervention time points in the HRV-ER trial. Effect sizes were derived from the pre-post difference in the HRV-ER older adult Osc+ (slow-paced breathing) group. We powered the study to detect small-to-medium effect sizes ($f = .2$) with a .7 correlation among repeated measures and aimed for 95% power at $\alpha = .05$. Based on these parameters, a total sample size of $N = 42$ (with three assessments) was required. Sixty-two participants (31 in each condition) ultimately completed the study.

3. Outcome Measures and Analyses

We examined condition differences (slow-paced breathing vs. random-paced breathing) in intervention-related change in the following outcome measures. The average time between pre and post intervention assessment was 10 weeks.

Primary outcome measures

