- **Change in plasma amyloid beta levels:** We computed an aggregate score based on plasma A β 40 and A β 42 levels (pg/mL), calculated as the average of their Z-scores. Higher values on this composite measure are associated with greater risk of Alzheimer's disease. This score was compared across three time points: Week 2 (pre-intervention), Week 7 (mid-intervention), and Week 12 (post-intervention). We conducted a time (Week 2, 7, 12) \times condition ANOVA to test for a time \times condition interaction in plasma A β levels, assessing group differences in change over time.
- **Change in plasma Ab42/40 ratio:** The plasma A β 42/40 ratio was calculated by dividing the plasma A β 42 concentration (pg/mL) by the plasma A β 40 concentration (pg/mL) at each time point. We conducted a time (Week 2, 7, 12) \times condition ANOVA to test for an interaction effect, using plasma A β 42/40 ratio scores as the dependent variable to assess group differences over time.

Secondary outcome measures

- **Change in brain perivascular space (pvs) volume:** PVS volume was defined as the percentage of PVS volume relative to white matter volume in the centrum semiovale, our main region of interest. To examine condition differences in changes over time, we conducted a time (Week 2, 7, 12) \times condition ANOVA to test for an interaction effect.

- **Change in hippocampal volume:** We tested whether there were condition differences in changes in hippocampal volume. We performed a two-way mixed ANCOVA on hippocampal volume, with condition (slow-paced vs. random-paced) as the between-subjects factor and time point (Week 2, 7, 12) as the within-subjects factor, controlling for intracranial volume as a covariate.
- **Brain training performance on 12 Lumosity games during the breathing intervention (controlling for brain training performance pre intervention):** Increments in game play performance over the course of the intervention were captured on latent level, with all games contributing to the latent variable. To evaluate longitudinal changes in cognitive performance during the intervention, we fitted a linear mixed-effects model to participants' latent performance scores across the 10 time bins. We examined condition differences in performance changes over time.

Other pre-specified outcome measures

- Change in plasma pTau-181/tau ratio:
- Change in urine Ab42

Safety outcomes

Six non-serious adverse events were reported and subsequently resolved.

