4. Populations and subgroups to be analyzed

Population analyzed is composed by all randomization subjects who completed assessments and whose data quality was sufficient for data analysis.

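### The only analysis population is randomised participants who completed and gave usable data; with no all-randomised analysis, the Week 2/7/12 comparisons are not fully protected by randomisation

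*SAP*

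**What the plan says.** SAP section 4 (Populations and subgroups to be analyzed) is a single sentence that restricts analysis to "all randomization subjects who completed assessments and whose data quality was sufficient for data analysis". It makes no exception for any outcome. Neither document defines an all-randomised set, a missing-data method, a missing-data sensitivity analysis, or what makes data quality sufficient.

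On timing, the Protocol (Research Objectives) asks for "9 weeks of paced breathing (starting Week 3) at home". The visit schedule puts blood, urine and MRI at Weeks 2, 7 and 12. In the section on the home intervention, the Protocol says "The feedback will differ between the two conditions": one arm is trained to maximise heart rate oscillations, the other to avoid them.

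On analysis, SAP section 3 uses a three-visit time by condition ANOVA for both primary outcomes (the amyloid composite and the Aβ42/40 ratio) and for perivascular space volume. Hippocampal volume has a mixed ANCOVA "with condition (slow-paced vs. random-paced) as the between-subjects factor and time point (Week 2, 7, 12) as the within-subjects factor". Only the Lumosity outcome has a different model: "To evaluate longitudinal changes in cognitive performance during the intervention, we fitted a linear mixed-effects model".

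On numbers, SAP section 2 reports "Sixty-two participants (31 in each condition) ultimately completed the study". The number randomised, in total or by arm, is not given.

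**The concern.** Randomisation makes the arms comparable as assigned. Attending at Weeks 7 and 12, and giving a usable sample or scan there, comes after the assigned breathing has begun. If the type of person lost differs between arms, the remaining groups can differ in amyloid or brain-volume change with no effect of breathing at all. Different tasks and opposing feedback goals make unequal loss possible; nothing in the documents shows that it happened.

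Two features add to the exposure. First, a repeated-measures ANOVA as usually fitted drops anyone missing one of the three visits. That is an inference about the software default, as the SAP does not say so. Second, the completion condition can be read per outcome or across all visits, so the excluded set cannot be identified.

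At stake is how the two primary results can be read: as an effect of assignment, or as a contrast among those retained.

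**Working it through.** **1. Is this a sample-size problem?** Inputs from SAP section 2: f = 0.2, correlation ρ = 0.7, m = 3 assessments, 95% power, α = 0.05; k = 2 arms; sphericity assumed. For the within-between interaction, λ = f²·N·m/(1−ρ), with (k−1)(m−1) and (N−k)(m−1) degrees of freedom.

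- N = 41: λ = 0.04 × 41 × 3/0.3 = 16.4, power 0.954. For equal arms this rounds to N = 42: λ = 16.8, power 0.959. The SAP's 42 is reproduced.
- N = 62: λ = 24.8, power 0.996.

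The issue is therefore bias, not precision.

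**2. How many people might be left out?** Not stated. If a share d of those randomised was excluded, 62/(1−d) were randomised. For d = 5, 10, 20 and 30% that is about 65, 69, 78 and 89 people, leaving out about 3, 7, 16 and 27.

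**3. General form of the bias.** Let d be the share excluded in an arm and g the completer-minus-excluded difference in mean change, in SD. The completer contrast differs from the all-randomised contrast by d₁g₁ − d₀g₀.

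- Same d and same g in both arms: 0.
- 20% v 10% excluded, g = 0.5 in both: 0.2 × 0.5 − 0.1 × 0.5 = 0.05 SD.
- 20% in each arm, g = +0.5 and −0.5: 0.10 + 0.10 = 0.20 SD.
- 30% in each arm, g = +1 and −1: 0.30 + 0.30 = 0.60 SD.

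**4. Yardsticks.** With unit SD, ρ = 0.7 and 31 per arm, the standard error of the arm difference in Week 2-12 change is √(2(1−0.7) × 2/31) = 0.197 SD. The planning effect f = 0.2, under a linear interaction with cell deviations ±a(−1, 0, 1), gives a = 0.2/√(2/3) = 0.245, so the arms differ in Week 2-12 change by 4a = 0.98 SD.

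**5. Illustrative simulation.** Assumptions (the documents neither support nor exclude them): no true effect, trivariate normal, unit SD, ρ = 0.7, loss in one arm only, logistic in the standardised Week 2-7 change. For type I error the affected arm starts with 33, 34 or 39 people, the other with 31. The sign depends on the arm and direction assumed.

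| Loss in one arm | 5% | 10% | 20% |
|---|---|---|---|
| Log-odds 1 per SD: Week 7 bias (SD) | −0.036 | −0.070 | −0.135 |
| Log-odds 1 per SD: Week 12 bias (SD) | −0.018 | −0.035 | −0.067 |
| Interaction type I error | 0.053 | 0.060 | 0.086 |
| Log-odds 0.5 per SD: Week 12 bias (SD) | −0.010 | −0.019 | −0.037 |
| Interaction type I error | 0.052 | 0.054 | 0.062 |

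Week 12 bias is half of Week 7 bias because the regression of the Week 2-12 change on the Week 2-7 change is (1−ρ)/(2(1−ρ)) = 0.5. With no loss, random one-arm loss, or the same mechanism in both arms, type I error is 0.048 to 0.053 (simulation error about 0.002).

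**6. What a mixed model leaves in** (log-odds 1 per SD, unstructured covariance, all available visits).

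| Pattern | Completer bias remaining |
|---|---|
| Leaves after an observed Week 7 | Week 12: about 0 |
| Leaves before Week 7 | Week 12: about 70%; Week 7: about 86% |
| Misses Week 7 only | Week 12: 0; Week 7: about 72% |
| Loss depends on the unseen Week 12 change | Week 12: about 72% |

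**7. Random failure of samples or scans.** If each visit fails independently with probability q, all three are present for (1−q)³ of people.

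| q | Complete on three visits | Rise in Week 2-12 SE: three-visit ANOVA | Mixed model |
|---|---|---|---|
| 2% | 94.1% | 3% | 1% |
| 5% | 85.7% | 8% | 4% |
| 10% | 72.9% | 17% | 8% |

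This costs precision but causes no bias.

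**The case against.** The strongest reply is that the harm is hypothetical. No passage shows loss, unequal loss or quality exclusions that depend on arm. The documents do not describe participants being told their plasma or MRI results, so direct selection on those changes is less natural than in a symptom trial. The illustrated Week 12 biases of 0.02 to 0.07 SD are about 2 to 7% of the 0.98 SD planning effect, and type I error moves appreciably only with 20% loss confined to one arm and the stronger selection. The Protocol describes reminders and contact when practice lapses, and expects high compliance. Section 4 excludes nobody for poor adherence. Finally, the mixed model is a partial cure, and would be post hoc in an SAP written in the past tense.

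Much of this stands: the size is unknown and may be nil, and the mixed model relies on missing-at-random. It does not remove the point. The planning effect is not a smallest important effect, and opposing selection in the two arms gives the larger figures in step 3. The compliance expectation comes from a 5-week study and concerns practice, not visit attendance. Links through health or tolerance of the task remain possible. Equal completer counts settle nothing without the numbers randomised. Exceeding the required 42 answers power, not selection.

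**Conclusion.** The concern holds. The SAP's sole population selects on events after randomisation, and no all-randomised analysis accompanies it. That much is certain from the text. Whether bias exists, its direction and its size cannot be determined from the documents. Under the one-arm scenarios driven by Week 2-7 change it is small at Week 12 (0.01 to 0.07 SD, against a standard error of 0.20 SD), with type I error between about 5% and 9%. It is zero under random loss, immaterial when both arms share the mechanism, and could be larger if selection runs in opposite directions. All these figures rest on assumed loss rates and mechanisms. The plan should be changed, because the remedy is cheap and the primary results depend on it; there is no evidence that they are wrong.

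**What to change.** - **Report the losses.** Tabulate, by arm and visit, the numbers randomised, lost, missing a sample or scan, and excluded for quality, with reasons. If losses are few and even, this largely settles the matter.
- **Main analysis.** All randomised participants with at least one usable assessment, by assigned arm. Fit a mixed model for repeated measures (visit, arm, visit by arm, unstructured covariance) to every available sample or scan, keeping intracranial volume for the hippocampus. The SAP already uses a mixed model for the Lumosity scores.
- **Quality exclusions.** Apply them per sample or scan, by a written rule, blind to arm.
- **Completer analysis.** Report the ANOVA or ANCOVA alongside. If it has already been run, label the mixed model post hoc.
- **Sensitivity.** If losses or exclusions differ by arm, add a delta-adjusted analysis, since the mixed model does not cure loss that depends on unobserved change.

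The cost is SAP wording and one extra model per outcome, with no new data collection. The model can use only material already collected and assayed; the documents do not say whether samples from non-completers were assayed.
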